2/3	
Current dose level has not been tolerated. Reduce dose to the lower dose level
If only 3 subjects have been treated at the lower dose level, accrue an additional 3 subjects at the lower dose level.If 6 subjects have already been treated at the lower dose level, the lower dose level is the MTD.If this occurs at dose level A, the study will be terminated early.
1/3 + 0/3 (1/6)	
Escalate dose. Accrue 3 new subjects at next highest dose level. If 0/6 or 1/6 DLTs at dose level C, then this is the MTD.
1/3 + 1/3 (2/6)	
Current dose level has not been tolerated. Reduce the dose. If this occurs at the lowest dose level, the study will be terminated early.

To be read with reference to Section 9.3 (page 22), above. Adapted from Koreth *et al.*⁵¹

9.4 Determination of Maximum Tolerated Dose.

The maximum tolerated dose (MTD) is the highest tolerated dose level at which a minimum of 6 subjects have been evaluated, with fewer than 2 evaluable subjects in 6 experiencing a dose limiting toxicity (DLT); i.e. DLT in $\leq 1/6$ evaluable subjects. **In addition to the above, at least 1 patient should meet the criteria for response or remission for it to be considered the MTD.**

Subjects will be considered unevaluable for DLT if they are removed from the study or die without developing DLT prior to receiving at least 8 weeks of IL-2 therapy. If there are fewer than 3 evaluable subjects in a cohort, additional subjects will be added at that dose level.

Intolerable lower grade toxicity that does not meet the definition of DLT, but still means that a subject is unable to complete the per-protocol treatment will be taken as equivalent to a DLT for the purpose of assessing dose escalation. If ≥ 2 subjects in a cohort of 3 refuse to continue at that dose level for at least 8 weeks due to intolerable lower grade toxicity, that dose level will not be regarded as the MTD.

9.5 Definition of Dose Limiting Toxicities.

Organ toxicities will be assessed at scheduled clinical visits and graded according to the National Cancer Institute Common Terminology Criteria for Adverse Events v4.0⁵⁴.

- (i). **Anaphylaxis:** Life threatening anaphylaxis due to the study drug is considered a DLT.
- (ii). **Grade 4 toxicity:** Grade 4 toxicity (except colitis, see below) directly related to IL-2 by week ~~11~~8 of IL-2 treatment is considered a DLT.

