- (iii). **Grade 3 toxicity:** IL-2 will be withheld for grade 3 toxicity (except colitis).
- (iv). **Development of a life-threatening infection:** Development of a life threatening infection, as assessed by the treating physician, prior to week 8 of IL-2 therapy will be considered a DLT. IL-2 will be withheld.
- (v). **Grade 2 renal toxicity:** IL-2 will be withheld in the event of a grade 2 renal toxicity (creatinine = 1.5-3.0 x ULN).

Development of toxic megacolon or colitis requiring immediate surgical intervention is a well-described risk of active UC. Consequently, it will not be considered a DLT. However, IL-2 will be discontinued.

9.6 Clinical Assessments for Toxicity.

Subjects will undergo regular clinical examination (history and physical examination), blood tests and other tests as indicated at scheduled visits in order to detect potential drug toxicity, as detailed in Section 11 (Page 31).

9.7 Extended Treatment with Low-Dose IL-2.

After completing 8 weeks of IL-2 therapy, subjects who have achieved a clinical response or entered remission (see Section 14, Page 43, for definitions) at any dose level and have an acceptable toxicity profile will be allowed to continue treatment at that dose level, at the discretion of the treating physician. These subjects will be seen in clinic every 3 months for a year, after which they will be followed by the referring gastroenterologist. Prometheus Laboratories will continue to supply IL-2 for up to one year after completing 8 weeks of IL-2 therapy to subjects who have achieved a clinical response or entered remission at any dose level and have an acceptable toxicity profile.

Subjects on extended duration IL-2 therapy will not be evaluable for toxicity and DLT endpoints. The addition of other medications (except the combination of sirolimus and tacrolimus) will be permitted at the discretion of the treating physician. Subject assessment while on extended treatment with IL-2 is detailed in Section 11.4 (page 34). In the event of toxicity attributable to IL-2, therapy will be discontinued.

10 STUDY DRUG: ALDESLEUKIN.

10.1 Formulation, Reconstitution and Storage.

Recombinant human IL-2 (aldesleukin, Proleukin®) is supplied free of charge by Prometheus Laboratories, Inc. (San Diego, CA).

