Soiffer et al. ⁵⁰	0.2-0.6x10 ⁶ IU/m ² /day	Enhance graft vs. leukemia effect following HSCT	29	Fatigue	15 (52)
				Temp >38°C	14 (48)
				Nausea/vomiting	11 (38)
				Myalgia	9 (31)
				Rash	9 (31)
				Diarrhea	7 (24)
				Edema	6 (21)
				Dyspnea	6 (21)
				Catheter infection	5 (17)
				Thyroid dysfunction	2 (7)
Koreth et al. ⁵¹	0.3-3x10 ⁶ IU/m ² /day	Treatment of steroid-resistant GvHD	28	Thrombocytopenia	2 (7)
				Injection site induration	3 (11)
				Infections*	3 (11)
				Renal failure**	2 (7)
				Renal dysfunction	1 (4)
				Flu-like symptoms	1 (4)
				Thrombocytopenia	1 (4)
Saadoun et al. ⁵²	1.5-3x10 ⁶ IU/day	Treatment of HCV-associated vasculitis	10	Fatigue	4 (40)
				Flu-like symptoms	4 (40)
				Injection site induration	2 (20)
				Arterial hypertension	1 (10)
				Myalgia	1 (10)

* Recurrent MRSA pneumonia (1), *Hemophilus influenzae* type-B bacteremia (1), MRSA furuncle (1)

** Thrombotic microangiopathic renal failure in two subjects taking tacrolimus and sirolimus. This is a recognized complication of this combination of medications.

11.8 Criteria for Treatment Discontinuation.

Subjects will be removed from the study and therapy with IL-2 should be abandoned for any of the following circumstances if they are deemed possibly, probably or definitely related to IL-2, or per subject preference:

- The subject withdraws his/her consent at any time.
- Anaphylactic reaction to IL-2.
- Life threatening infection on IL-2.
- Other grade 4 toxic event.
- Grade 3 toxicity.
- Grade 2 renal toxicity.
- The development of toxic megacolon or colitis requiring immediate surgical intervention.
- At the discretion of the treating physician.

11.9 Dose Modification/Toxicity Management.

In the event of IL-2 related toxicity that does not meet the requirement for treatment discontinuation (grade 2 toxicity or less, excluding grade 2 renal toxicity), the treating physician may elect to withhold IL-2 to allow the toxicity to resolve. IL-2 can be recommenced at 50% of the target dose if the toxicity resolves to grade 1 or better within 2 weeks. At the discretion of the treating physician, if re-introduction of IL-2 is tolerated by the subject, the dose of can be escalated to the target dose.

12 REPORTING OF UNANTICIPATED PROBLEMS INVOLVING RISKS TO RESEARCH SUBJECTS, INCLUDING ADVERSE EVENTS.

12.1 Reporting to the Principal Investigator.

The following events will be reported to the principal investigator within 24 hours of being known:

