A Data Safety and Monitoring Board (DSMB) has been constituted. The DSMB members are as follows: [name] MD PhD (Chair, Gastroenterologist, University of North Carolina at Chapel Hill), [name] MB BS MPH (Gastroenterologist, Massachusetts General Hospital), and [name] PhD (Statistician, Boston Children's Hospital). The DSMB will determine stopping points for individual subjects and the study as a whole. In addition, the DSMB will determine the schedule of meetings in order to review subject safety information and will also make recommendations concerning the continuation, modification or termination of the study.

The DSMB will review study data and make recommendations on the conduct of the study at the following time points:

- In the event of any serious adverse events or DLT.
- When the third subject completes 8 weeks of IL-2 treatment, as per protocol.
- Three months after study initiation.
- Six months after study initiation.
- At six month intervals thereafter.

14 STUDY ENDPOINTS.

Subjects will be periodically assessed as described in Section 11 (page 31) in order to determine if the primary and secondary endpoints have been met.

14.1 Determination of Safety of Daily SC Low Dose IL-2.

The safety of daily low-dose IL-2 will be determined by assessing for potential side-effects and dose limiting toxicity at each study visit.

14.2 Determination of the Maximum Tolerated Dose of Daily SC Low Dose IL-2.

The MTD will be determined using the dose escalation strategy and assessments described in Sections 9 and 11 (pages 21 and 31, respectively).

14.3 Determination of the Feasibility of Administering an Eight Week Course of Daily SC Low Dose IL-2 in Subjects with Moderate to Severe UC.

This relates to the technical feasibility of administering daily low-dose SC IL-2 as per protocol. The narrative report of this outcome will include the numbers of subjects enrolled, subjects who completed the protocol and a description of any barriers to the technical feasibility of this approach in subjects with UC.

14.4 Determination of the Clinical Response to Daily SC Low Dose IL-2.

Mayo score^{7,55} (Table 5; page 44) will be assessed as per protocol between weeks -2 and 0 (as close to week 0 as possible) and week 8 in order to determine clinical response. Moderate to severe UC, denoted by a Mayo score of 6-12 is an inclusion criterion. Clinical response and remission are defined according to Rutgeerts *et al.*⁷

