14.4.1 Definition of Clinical Response.

“A decrease from baseline in the total Mayo score of at least 3 points and at least 30% , with an accompanying decrease in the subscore for rectal bleeding of at least 1 point or an absolute subscore for rectal bleeding of 0 or 1.”⁷

14.4.2 Definition of Remission..

“A total Mayo score of 2 points or lower, with no individual subscore exceeding 1 point.”⁷

14.4.3 Definition of Mucosal Healing.

“An absolute subscore for endoscopy of 0 or 1.”⁷

14.5 Assessment of the Immunological Response to IL-2 Therapy.

Data obtained from research laboratory-based assessment of subject immune responses to IL-2 therapy, that do not have direct clinical relevance, will be reported as appropriate for each data type.

Table 5: Mayo Scoring System for Assessment of Ulcerative Colitis Activity.^{7,55}

Stool frequency*	
0	Normal no. of stools for this subject
1	1 to 2 stools more than normal
2	3 to 4 stools more than normal
3	5 or more stools more than normal
Rectal bleeding**	
0	No blood seen
1	Streaks of blood with stool less than half the time
2	Obvious blood with stool most of the time
3	Blood alone passes
Findings on endoscopy	
0	Normal or inactive disease
1	Mild disease (erythema, decreased vascular pattern, mild friability) ^[1,2]
2	Moderate disease (marked erythema, lack of vascular pattern, friability, erosions) ^[1,2]
3	Severe disease (spontaneous bleeding, ulceration)
Physician’s global assessment	
0	Normal
1	Mild disease
2	Moderate disease

3 Severe disease

- * Each subject serves as their own control.
- ** Represents the most severe bleeding of the day.

15 STATISTICAL CONSIDERATIONS.

The primary endpoint of this Phase I study is to determine the MTD of daily subcutaneous IL-2 in moderate to severe UC.

15.1 Probability of Dose Escalation Under Various DLT Rates.

Table 6 shows the probability of escalation under various true DLT rates. With this design, there is 91% probability of escalation if the true rate of DLT is 10% and 17% probability of escalation if the true DLT rate is 50%.

Table 6: Probability of Dose Escalation	
True rate of DLT	Probability of dose escalation
10%	0.91
20%	0.71
30%	0.49
40%	0.31
50%	0.17
60%	0.08

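### Severe colitis judged to be caused by IL-2 is kept out of the DLT count and the subject is replaced, so it cannot affect the written MTD decision

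*Combined protocol and SAP*

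**What the plan says.** Five rules bear on this point.

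- **Section 9.5(ii), grade 4 rule.** The DLT definition covers "Grade 4 toxicity (except colitis, see below) directly related to IL-2". The clause is limited to events attributed to the drug, so its exception removes events already so attributed.
- **Section 9.5, closing paragraph.** Toxic megacolon or colitis needing immediate surgery is described as a known risk of active UC. The text continues: "Consequently, it will not be considered a DLT. However, IL-2 will be discontinued". No attribution test is given.
- **Section 11.8, removal.** Subjects leave the study for surgical colitis, or for any other grade 4 toxic event, "if they are deemed possibly, probably or definitely related to IL-2".
- **Section 9.4, evaluability and replacement.** "Subjects will be considered unevaluable for DLT if they are removed from the study or die without developing DLT" before 8 weeks of therapy. Then: "If there are fewer than 3 evaluable subjects in a cohort, additional subjects will be added at that dose level".
- **Section 9.4, lower-grade rule.** Intolerable lower-grade toxicity that prevents a subject from completing treatment "will be taken as equivalent to a DLT for the purpose of assessing dose escalation". This sentence mentions colitis neither as included nor as excepted.

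Section 13 has the DSMB review data "In the event of any serious adverse events or DLT" and set stopping points for single subjects and for the trial. Section 15 names the MTD as the primary endpoint.

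**The concern.** Background risk is a good reason not to charge a dose with colitis caused by the disease. It is not a reason to leave out colitis that the investigator has attributed to the drug. The exemption covers both kinds. Because the subject is also replaced, the event leaves the denominator as well as the numerator.

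What is at stake is the primary endpoint, and the ten further subjects who are treated at whatever dose is declared the MTD (9.3.4). The colon is the diseased organ, so colitis is the adverse effect a reader would most want the dose decision to reflect. The background gives some reason to watch for it. Treg selectivity is lost in vitro at higher IL-2 concentrations (4.4). Diarrhea was seen in 24% of the low-dose intravenous study (4.6). Level C is 1.5 times the MTD of the earlier subcutaneous GvHD study (9.2). None of this shows that IL-2 worsens UC at these doses.

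**Working it through.** **1. The plan's own figure.** Section 15.1 states "there is 91% probability of escalation if the true rate of DLT is 10" percent. For a 3+3 design with DLT probability p,

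f(p) = (1−p)³ + 3p(1−p)² × (1−p)³.

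At p = 10, 20, 30, 40, 50 and 60% this gives 0.906, 0.709, 0.494, 0.309, 0.172 and 0.082. Table 6 is reproduced at all six rates, and it describes counted DLTs only.

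**2. A case that needs no assumed rate.** Three subjects start at a level. Two develop colitis that needs immediate surgery before week 8, judged related to IL-2, and the third completes without a DLT.

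- Neither case is a DLT (9.5). Both subjects are removed (11.8) and are unevaluable (9.4).
- The count is 0 DLTs in 1 evaluable subject. With fewer than 3 evaluable, two more subjects are added at the same dose.
- Had both events been any other grade 4 toxicity directly related to IL-2, the count would be 2/3 and the dose would not be tolerated (Table 2).

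**3. Effect on the operating characteristics.** Let d be the rate of other DLTs and c the rate of IL-2-related severe colitis, taken as mutually exclusive. The documents give neither. I take d = 10% (a Table 6 row) and c = 5% to 30%. This assumes that all these colitis cases fall under the exemption and occur before week 8.

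- As written, the cases are replaced, so the DLT rate among evaluable subjects is d/(1−c).
- If they counted, the rate would be d + c.
- Level C passes its DLT rule with at most 1 DLT in 6: g(p) = (1−p)⁶ + 6p(1−p)⁵.

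| c | d/(1−c) | f as written | f if counted | g as written | g if counted |
|---|---|---|---|---|---|
| 5% | 0.105 | 0.897 | 0.814 | 0.875 | 0.776 |
| 10% | 0.111 | 0.887 | 0.709 | 0.863 | 0.655 |
| 20% | 0.125 | 0.862 | 0.494 | 0.833 | 0.420 |
| 30% | 0.143 | 0.828 | 0.309 | 0.793 | 0.233 |

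Sensitivity to d at c = 10%: escalation is 1.00 against 0.906 at d = 0, 0.968 against 0.814 at d = 5%, and 0.660 against 0.494 at d = 20%. With no other DLTs, escalation as written is certain whatever c is.

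**4. Escalating past two or more uncounted removals.** The chance of at least 2 removals while accruing k evaluable subjects is

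h(k) = 1 − (1−c)^k (1 + kc).

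Escalation happens after 3 or after 6 evaluable subjects, so with p = d/(1−c) the joint probability is (1−p)³h(3) + 3p(1−p)⁵h(6). At c = 10% this is 0.702 × 0.052 + 0.185 × 0.150 = 0.064. At c = 5, 20 and 30% it is 0.018, 0.203 and 0.352.

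**5. Where the text can be read two ways.**

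- *Grade 4 exception.* Its cross-reference points to a paragraph that covers only megacolon and surgical cases. On the narrow reading, IL-2-related grade 4 colitis without surgery is still a DLT. The surgical cases are excluded on either reading.
- *Lower-grade rule.* Read literally, milder colitis that stops treatment counts as a DLT equivalent while surgical colitis does not. If the 9.5 exemption carries into 9.4, no colitis counts.
- *Grade 3 colitis.* 9.5(iii) excepts it from withholding, but 11.8 discontinues for grade 3 toxicity with no colitis exception. Its status under 9.4 is unclear.
- *Infection route.* A case that also met the life-threatening infection rule, 9.5(iv), would count, but as an infection.

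**The case against.** The best defense is that the exemption was a reasoned choice. Every subject has active moderate-to-severe UC, there is no control arm, and attributing a flare to the drug is hard in this setting. If natural severe flares in 10% of subjects were all wrongly attributed to IL-2, with 10% other DLTs, escalation would fall from 0.89 to 0.71 for no safety gain. This stands as a real cost of the fix. It does not justify exempting events that have been attributed to the drug, and every other organ already faces the same judgment.

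The plausibility evidence is also thin. The 24% diarrhea came from continuous intravenous infusion after bone marrow transplant. Section 4.6 says subcutaneous dosing gives 20- to 30-fold lower peaks, and the two subcutaneous studies in Table 4 (28 and 10 subjects) list neither diarrhea nor colitis. So the contrasts above illustrate the rule and do not predict its effect.

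The DSMB is a genuine safeguard. It reviews any serious adverse event, so it should see the first such case. It does not alter the MTD count, however, and the plan gives it no colitis threshold. The added MTD requirement of at least one response or remission (9.4) is a weak check on toxicity.

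A reader might infer that the rule plainly runs backwards, with mild colitis counting and severe colitis not. That is only one reading of 9.4, which never names colitis. An example built on grade 3 colitis would rest on the conflict between 9.5(iii) and 11.8.

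**Conclusion.** The point holds for toxic megacolon and surgical colitis on any reading. It holds for other IL-2-related grade 4 colitis on the wording of 9.5(ii), subject to the cross-reference. Colitis judged directly related to IL-2 can be severe enough to require immediate surgery and still have no effect on the written dose decision. Only DSMB action outside the 3+3 rule would stop escalation.

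The size depends on a rate the documents do not give. With 10% other DLTs and IL-2-related severe colitis in 5% to 30%, escalation is 0.90 to 0.83 as written against 0.81 to 0.31 if counted. Level C passing its 6-subject rule is 0.88 to 0.79 against 0.78 to 0.23.

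The documents do not support two stronger conclusions: that IL-2 at these doses causes severe colitis, or that such events would go unreviewed. Table 6 is arithmetically correct for what it counts. The plan should be changed because the primary endpoint is affected and the change is small. DSMB review keeps this from being more serious.

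**What to change.** 1. In 9.5, count grade 4 colitis, toxic megacolon or colitis needing immediate surgery as a DLT when judged directly related to IL-2, the test already used for other grade 4 toxicity. Keep the exemption for events not so judged.
2. In 9.4, state that the lower-grade rule includes colitis judged related to IL-2.
3. Tabulate by dose level all treated subjects, evaluable or not, who stop IL-2 before week 8 for colitis or UC worsening not counted as a DLT. If 2 or more do so at one level, require DSMB review before opening the next level or declaring the MTD.

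The cost in text is three sentences and one count from data already collected, with no new visits or tests. The cost in conduct is some misattributed flares, as sized above, and some review holds. Using h(k) from the working, with c now the rate of stopping for uncounted flares:

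| Stopping rate | Hold, 3 evaluable | Hold, 6 evaluable |
|---|---|---|
| 5% | 1.4% | 4.4% |
| 10% | 5.2% | 15% |
| 20% | 18% | 42% |
| 30% | 35% | 67% |

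At the higher rates holds would be common, so the sponsor should agree a quick review procedure with the DSMB in advance. A hold is a review and does not by itself lower the dose.

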While the study design of this proposed phase Ib/Ila clinical trial is based on Koreth *et al*'s study, patients with active UC are likely to be fitter than patients with steroid-resistant GvHD following BMT. In a recent study with a more comparable group, Saadoun *et al*.⁵² treated 10 patients with HCV-associated vasculitis that was unresponsive to conventional anti-viral therapy and/or rituximab with low-dose IL-2: 1.5 MIU/day for 5 days, followed by three 5-day courses of 3 MIU/day at weeks 3, 6 and 9. Only mild (grade 1) toxicities were observed, including fatigue (4/10), flu-like symptoms (4/10), SC injection site reaction (2/10), arterial hypertension (1/10) and myalgia (1/10).

4.7 Hypothesis.

Based on these data, we hypothesize that low-dose IL-2 will safely expand PB and LP Tregs *in vivo* in patients with UC and be efficacious in controlling disease.

5 STUDY DESIGN AND OBJECTIVES.

5.1 Study Design.

An open-label, phase Ib/IIa clinical trial, with a 3+3 dose escalation design, to determine the safety and the maximum tolerated dose (MTD) of daily SC recombinant human interleukin-2 (IL-2, aldesleukin, Proleukin®) in adult subjects with moderate to severe UC.

5.2 Primary Objectives.

- (i). To determine the safety of daily SC low dose IL-2 in subjects with moderate to severe UC
- (ii). To determine the MTD of daily SC low dose IL-2 in subjects with moderate to severe UC.

5.3 Secondary Objectives.

- (i). To determine the feasibility of administering an eight week course of daily SC low dose IL-2 to subjects with moderate-to-severe UC.
- (ii). To determine the clinical response to the above treatment.
- (iii). To assess the immunological response to the above treatment, with particular reference to numbers and function of T_{regs} in the blood and intestinal lamina propria (LP)

6 SUBJECT SELECTION.

6.1 Inclusion Criteria.

- (i). Age 18-70 years. Maximum age limit for subjects recruited at BCH will be 30 years.
- (ii). A diagnosis of UC made by standard clinical, radiological, endoscopic and histological criteria.
- (iii). Moderate to severe UC with a Mayo score of 6-12.

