Data support the stability and sterility of reconstituted diluted aldesleukin preparations (reconstituted with SWFI and further diluted with D5W); and the stability and sterility of product reconstituted with SWFI but not further diluted, for up to 14 days at 2-8°C (36-46°F) when syringes are prepared by qualified health-care professionals under aseptic conditions⁴⁰. Therefore, if reconstitution and dilution are performed under controlled and validated conditions using a laminar flow hood, the dose or doses thus prepared and stored at 2-8°C (36-46°F) need to be used within 14 days.

On 4/26/2016, the Investigational Drug Service (IDS) at Brigham & Women's Hospital, Boston MA, reduced the beyond use dating for aldesleukin that is prepared at their research pharmacy for this study from 14 days to 9 days. **Consequently, aldesleukin prepared at BWH IDS and subsequently stored at 2-8°C (36-46°F) needs to be used within 9 days.**

10.4 Dosage.

Aldesleukin will be given according to the dose schema described in Section 9.2 (page 21), based on the cohort into which they are accrued. The first two subjects to receive IL-2 will be admitted overnight to the Clinical Translational Study Unit (CTSU). Aldesleukin may be administered in the home or out-subject setting by daily subcutaneous injection for 8 weeks. Subjects who receive additional treatment after experiencing clinical benefit from 8 weeks of

initial therapy may continue aldesleukin therapy at their initial dose level. They will be followed by their physician according to Section 9.7 (page 27).

10.5 Administration.

The product should be inspected visually for particulate matter or discoloration and brought to room temperature before administration. Administer as a subcutaneous injection. DO NOT ADMINISTER AS INTRAVENOUS PUSH OR BOLUS. Premedications are not required prior to the first dose or escalated doses.

11 CLINICAL AND LABORATORY EVALUATIONS.

Participants will have 10 face-to-face encounters with research staff throughout the clinical trial, including (i) Screening at week -2, (ii) Baseline assessment prior to first dose (day 0), (iii) Clinical assessment prior to second dose (day 1), (iv-viii) Assessments at day 4 optional visit) and weeks 1, 2, 4 and 6, (ix) End of treatment assessment at week 8, and (x) End of study assessment at week 12. On completion of the study, research staff will contact participants by telephone monthly for 2 months and on a 2-monthly basis for a further two months.

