- Serum chemistries: glucose, BUN, creatinine, uric acid, total bilirubin, alkaline_{SE}phosphatase, LDH, total protein, albumin, AST, ALT, and calcium (routine).
- Thyroid function tests (TSH, T3, free T4).
- Immunology bloods: Quantitative flow cytometric assessment of leucocytes, NK cells and Treg subsets from PB. Assessment of PB and LP Treg function. Banking of PBMCs, plasma, RNA, DNA.
- Microbiology: Stool sample and mucosal biopsies for analysis of the intestinal microbiome.
- IL-2 serum levels and anti-aldesleukin antibodies.

11.4 Evaluation of Subjects Undergoing Extended Treatment with Low Dose IL-2.

Patients with a treatment response who elect to undergo extended treatment (as described in Section 9.7, page 27) will be seen in clinic every 3 months as part of their routine clinical care. Evaluation may include:

- Medical history and physical examination, including assessment of symptoms and signs in order to detect potential drug toxicity (routine).
- Hematology: Complete blood count (CBC) and differential (routine).
- Inflammatory markers: ESR and CRP (routine).
- Serum chemistries: glucose, BUN, creatinine, uric acid, total bilirubin, alkaline_{SE}phosphatase, LDH, total protein, albumin, AST, ALT, and calcium (routine).
- Immunology bloods: Quantitative flow cytometric assessment of leucocytes, NK cells and Treg subsets from PB. Assessment of PB and LP Treg function. Banking of PBMCs, plasma, RNA, DNA.

11.5 Details of Specific Assays.

Routine laboratory tests will be performed at Boston Children's Hospital, Labcorp or other facilities according to availability.

The techniques required for immune phenotyping (e.g. FACS, PCR etc.) will be performed on appropriately collected samples at the [name] Laboratory at Boston Children's Hospital, the Harvard Digestive Disease Center and collaborating laboratories. The laboratory personnel who will perform these assays will be identified and/or appointed prior to the inception of this study. The specific protocols for each investigation, including the number of cells needed for each assay and precise locations and numbers of endoscopic biopsies etc., will be placed in the Trial Master File. A maximum of 26 biopsies will be obtained from each participant at each endoscopy for the purpose of these investigations, as described in Section 11.1 (page 31).

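### Section 9.7 excludes extended IL-2 treatment from toxicity as well as DLT endpoints, so non-serious expected toxicity beyond 8 weeks enters no safety summary

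*Combined protocol and SAP*

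**What the plan says.** Core treatment is 8 weeks of daily injections (Section 10.4: "Aldesleukin may be administered in the home or out-subject setting by daily subcutaneous injection for 8 weeks"). Section 9.7 then allows an extension. Subjects in response or remission "at any dose level and have an acceptable toxicity profile will be allowed to continue treatment at that dose level", at the treating physician's discretion. On supply: "Prometheus Laboratories will continue to supply IL-2 for up to one year after completing 8 weeks of IL-2 therapy". On follow-up: "These subjects will be seen in clinic every 3 months for a year". Other medications may be added, with one combination excepted, and IL-2 is stopped for attributable toxicity. The same section sets the analysis rule: "Subjects on extended duration IL-2 therapy will not be evaluable for toxicity and DLT endpoints".

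Four other places bear on that rule:

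- Section 5.2, primary objective (i): "To determine the safety of daily SC low dose IL-2 in subjects with moderate to severe UC". No duration is attached. The feasibility objective in Section 5.3, by contrast, is tied to the eight-week course.
- Section 14.1: "The safety of daily low-dose IL-2 will be determined by assessing for potential side-effects and dose limiting toxicity at each study visit". Section 11.2 lists week 12 among the visits with a history and examination directed at toxicity.
- Section 11.4 introduces the content of the 3-monthly extension visits with "Evaluation may include", so even the toxicity history is optional.
- Section 15.1 bases the toxicity rate on the 10 additional subjects at the MTD and mentions no extension summary.

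**The concern.** The exclusion covers two things that deserve different treatment. The DLT half follows from the design, because DLTs are counted over the 8-week course. The toxicity half has no such basis. It takes the only on-drug experience beyond 8 weeks out of an endpoint that serves a primary objective with no time limit.

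It also collides with the visit schedule. A subject who continues without a break is on IL-2 at week 12. Sections 14.1 and 11.2 count that visit for safety, and Section 9.7 says the subject is not evaluable for toxicity.

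What is at stake is the trial's ability to say anything systematic about longer dosing. The protocol itself treats some effects as not confined to early treatment: it follows anti-aldesleukin antibodies, if detected, past week 12 (Section 11.6). Table 4 also lists toxicities, such as fatigue and injection-site induration, that would usually be expected and non-serious if they recurred in the extension. Those are the events for which no summary is planned.

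**Working it through.** **The plan's own figure.** The documents give no exposure figure. The related figure is the precision of the toxicity rate in Section 15.1, a 90% interval within ±26% for n = 10. By the normal approximation at a rate of 0.5, 1.645 × √(0.25/10) = 0.260. It reproduces, and nothing below alters it.

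**Where an extension toxicity would be captured**

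| Route | Covers the extension? | Gives an aggregate summary? |
|---|---|---|
| 12.1 and 12.2: deaths, unexpected related events, other unanticipated problems | Yes, no 8-week limit | No |
| 12.3: serious adverse event reports to the drug supplier | Yes | No |
| 13: DSMB review after any serious event or DLT, and six-monthly | Yes | None specified |
| 9.7: stopping IL-2 for attributable toxicity | Yes | No |
| 14.1: safety endpoint | Week 12 yes; 3-monthly visits unclear | Overridden by 9.7 |
| 15.1: toxicity rate | No, 10 subjects at the MTD | Not for the extension |

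A non-serious, expected toxicity in the extension appears in no summary that the documents define.

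**Size of the excluded exposure.** Inputs:

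- Core treatment of 8 weeks (10.4), assumed complete for every subject.
- Extension of E weeks, with a ceiling of 52 (9.7).
- Proportion continuing, r. The documents do not give it; 10% to 50% is assumed.
- E is also unknown below the ceiling; 13, 26 and 52 weeks are assumed.

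Excluded share of all subject-weeks = E·r / (8 + E·r). The number of subjects cancels.

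| r | E = 13 | E = 26 | E = 52 |
|---|---|---|---|
| 10% | 1.3/9.3 = 14% | 2.6/10.6 = 25% | 5.2/13.2 = 39% |
| 20% | 2.6/10.6 = 25% | 5.2/13.2 = 39% | 10.4/18.4 = 57% |
| 30% | 3.9/11.9 = 33% | 7.8/15.8 = 49% | 15.6/23.6 = 66% |
| 40% | 5.2/13.2 = 39% | 10.4/18.4 = 57% | 20.8/28.8 = 72% |
| 50% | 6.5/14.5 = 45% | 13/21 = 62% | 26/34 = 76% |

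The excluded part is a majority when E·r > 8, that is r > 8/E:

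- 8/52 = 15.4% if all continuers stay the full year
- 8/26 = 30.8% at 26 weeks
- 8/13 = 61.5% at 13 weeks

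In head counts, Table 1 projects 3 + 3 + 16 = 22 subjects, or 22 × 8 = 176 core weeks. Four full-year continuers (4 × 52 = 208) exceed that; three (156) do not. At the upper limit of 28 subjects in Section 15.2, core exposure is 224 weeks. Five full-year continuers (260) exceed it; four (208) do not.

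**The case against.** The strongest defence is that this is an endpoint rule in a phase I MTD study, and the extension is in effect continued access. Continuers are selected for response and for tolerating the drug, and they may add other medications, so pooling them into the 8-week toxicity rate would bias it. Section 11.4 describes the 3-monthly visits as routine care, and scheduled study visits end at week 12. No sentence forbids describing extension events. This stands as a reason to keep the extension out of the DLT/MTD endpoint and the Section 15 rate. It does not justify removing it from toxicity altogether: a separate table meets the selection problem, and week 12 is a study visit on any reading.

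Three stronger readings are tempting, and the documents support none of them:

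- **That safety monitoring stops after week 8.** It does not. Death and serious-event reporting, DSMB review and stopping for attributable toxicity all continue.
- **That most of the drug exposure is discarded.** That needs more than 15.4% of subjects to stay a full year, or a larger proportion to stay for less. The documents give neither figure. Subject-weeks also overstate the information lost, because the extension is observed only every 3 months.
- **That responders lose their first 8 weeks of data,** because the sentence names subjects and not a period. Section 9.4 makes a subject unevaluable for DLT only on leaving or dying without a DLT before 8 weeks of therapy, and only those who complete 8 weeks can extend. The wording is loose, but that result is not the evident intent.

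**Conclusion.** The point holds for the word toxicity in Section 9.7, and not for DLT. As written, the rule keeps extension toxicity out of primary objective (i) and contradicts Sections 14.1 and 11.2 at week 12 for subjects who continue without a break. The practical loss is any aggregate account of non-serious, expected toxicity beyond 8 weeks.

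Its share of total exposure runs from about 14% to 76% over the assumed 10-50% uptake and 13-52 weeks. It is a majority only in part of that range. Whatever the share, it is all of the trial's exposure beyond 8 weeks. The figures rest on assumed uptake and duration and on full 8-week dosing in the core. No escalation decision, MTD determination or Section 15 estimate changes.

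**What to change.** Three edits:

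1. **Section 9.7.** Replace the sentence with: *the extension period will not be evaluable for the DLT/MTD endpoint or the Section 15 toxicity rate; data from the first 8 weeks remain evaluable.*
2. **Section 14.1.** Add that adverse events recorded from week 8 on extended treatment, including week 12 and the 3-monthly visits, are graded by CTCAE. They are tabulated descriptively by dose level and time on drug, in a separate table that shows subject-weeks of exposure and is not pooled with the 8-week rate.
3. **Section 11.4.** Make the recording of adverse events from the history and examination at those visits required. Without this the table would be incomplete. Laboratory tests can stay as planned.

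The visits are already planned, so sample size, dosing and MTD rules are untouched. The cost is wording, some data entry, and a required research record at what are now routine-care visits. The table will describe selected responders seen every 3 months, some on added medications, so it supports description and not a comparison of rates.
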